7.0 REGISTRATION PROCEDURES

7.1 General Guidelines

Prior to registration and any study-specific evaluations being performed, all patients must have given written informed consent for the study and must have completed the pre-treatment evaluations. Patients must meet all of the eligibility requirements listed in Section 3. Eligible patients will be entered on study centrally by the University of Chicago study coordinator. All sites should call the study coordinator at [contact] or [contact] to verify availability of a slot.

7.2 Registration Process

When a potential patient has been identified, notify the CRA via phone or email to ensure a reservation on the study ([contact] or [contact]). Reservations for potential subjects will only be held for subjects who have signed consent for that particular study.

When registering a subject, the following must occur:

- Confirm that the institution has a current IRB approval letter for the correct version of protocol/consent and has an annual update on file, if appropriate.
- Submit all required materials (Eligibility Checklist, Source documentation, & signed consent form) to confirm eligibility and required pre-study procedures to the CRA a minimum of 48 hours prior to the subject's scheduled therapy start date.
- Source documentation includes copies of all original documents that support each inclusion/exclusion criteria. The eligibility checklist does not serve as source documentation but rather as a checklist that original source documentation exists for each criterion.
- Communicate with the CRA to ensure all necessary supporting source documents are received and the potential subject is eligible to start treatment on schedule. If there are questions about eligibility, the CRA will discuss it with the PI. PI may clarify, but not overturn, eligibility criteria.
- Affiliate sites must confirm registration of subjects by obtaining a subject study ID number from the CRA via phone, fax or email.
- If a subject does not start on the scheduled day 1 treatment date, promptly inform the CRA as the delay in start may deem the subject ineligible and/or require further or repeat testing to ensure eligibility.
- The date the patient receives treatment for the first time will be considered the patient's "OnStudy Date." The patient's subject ID will be assigned and a confirmation of registration will be issued by the CRA on this date. Subjects that sign consent and do not go "OnStudy"

will be recorded in the database with the date they signed consent and the reason for not going "OnStudy" (e.g., Ineligible, Screen Failure or Withdrawn Consent).

8.0 TRIAL PROCEDURES

8.1 Trial Procedures

The Trial Flow Chart - Section 6.0 summarizes the trial procedures to be performed at each visit. Individual trial procedures are described in detail below. It may be necessary to perform these procedures at unscheduled time points if deemed clinically necessary by the investigator.

Furthermore, additional evaluations/testing may be deemed necessary by the Principal Investigator for reasons related to subject safety. In some cases, such evaluation/testing may be potentially sensitive in nature (e.g., HIV, Hepatitis C, etc.), and may require that additional informed consent be obtained from the subject.

8.1.1 Administrative Procedures

8.1.1.1 Informed Consent

The Investigator must obtain documented consent from each potential subject prior to participating in a clinical trial.

8.1.1.1.1 General Informed Consent

Consent must be documented by the subject's dated signature or by the subject's legally acceptable representative's dated signature on a consent form along with the dated signature of the person conducting the consent discussion.

A copy of the signed and dated consent form should be given to the subject before participation in the trial.

The initial informed consent form, any subsequent revised written informed consent form and any written information provided to the subject must receive the IRB approval/favorable opinion in advance of use. The subject or his/her legally acceptable representative should be informed in a timely manner if new information becomes available that may be relevant to the subject's willingness to continue participation in the trial. The communication of this information will be provided and documented via a revised consent form or addendum to the original consent form that captures the subject's dated signature or by the subject's legally acceptable representative's dated signature.

Specifics about a trial and the trial population will be added to the consent form template at the protocol level.

The informed consent will adhere to IRB requirements as well as applicable laws and regulations.

8.1.1.2 Inclusion/Exclusion Criteria

All inclusion and exclusion criteria will be reviewed by the investigator or qualified designee to ensure that the subject qualifies for the trial.

8.1.1.3 Medical History

A medical history will be obtained by the investigator or qualified designee. Medical history will include all active conditions, and any condition diagnosed within the prior 10 years that are considered to be clinically significant by the Investigator. Details regarding the disease for which the subject has enrolled in this study will be recorded separately and not listed as medical history.

8.1.1.4 Prior and Concomitant Medications Review

8.1.1.4.1 Prior Medications

The investigator or qualified designee will review prior medication use, including any protocol-specified washout requirement, and record prior medication taken by the subject within 28 days before starting the trial. Treatment for the disease for which the subject has enrolled in this study will be recorded separately and not listed as a prior medication.

8.1.1.4.2 Concomitant Medications

The investigator or qualified designee will record medication, if any, taken by the subject during the trial. All medications related to reportable SAEs should be recorded as defined in Section 7.2.

8.1.1.5 Disease Details and Treatments

8.1.1.5.1 Disease Details

The investigator or qualified designee will obtain prior and current details regarding disease status.

8.1.1.5.2 Prior Treatment Details

The investigator or qualified designee will review all prior cancer treatments including systemic treatments, radiation and surgeries.

8.1.1.5.3 Subsequent Anti-Cancer Therapy Status

The investigator or qualified designee will review all new anti-neoplastic therapy initiated after the last dose of trial treatment. If a subject initiates a new anti-cancer therapy within 30 days after the last dose of trial treatment, the 30 day Safety Follow-up visit must occur before the

first dose of the new therapy. Once new anti-cancer therapy has been initiated the subject will move into survival follow-up.

8.1.1.6 Adverse Event (AE) Monitoring

The investigator or qualified designee will assess each subject to evaluate for potential new or worsening AEs as specified in the Trial Flow Chart and more frequently if clinically indicated. Adverse experiences will be graded and recorded throughout the study and during the follow-up period according to NCI CTCAE Version 4.0 (see Section 11.2). Toxicities will be characterized in terms regarding seriousness, causality, toxicity grading, and action taken with regard to trial treatment.

For subjects receiving treatment with pembrolizumab all AEs of unknown etiology associated with pembrolizumab exposure should be evaluated to determine if it is possibly an event of clinical interest (ECI) of a potentially immunologic etiology (termed immune-related adverse events, or irAEs).

Please refer to section 7.2 for detailed information regarding the assessment and recording of AEs.

8.1.1.7 Physical Exam

The investigator or qualified designee will perform a physical exam at protocol specified time points as per the Trial Flow Chart (Section 6.0). Clinically significant abnormal findings should be recorded as medical history. A full physical exam should be performed during screening,

8.1.1.8 Vital Signs

The investigator or qualified designee will take vital signs at screening, prior to the administration of each dose of trial treatment and at treatment discontinuation as specified in the Trial Flow Chart (Section 6.0). Vital signs should include temperature, pulse, respiratory rate, weight and blood pressure. Height will be measured at screening only.

8.1.1.9 Eastern Cooperative Oncology Group (ECOG) Performance Scale

The investigator or qualified designee will assess ECOG status (see Section 13.1) at screening, prior to the administration of each dose of trial treatment and discontinuation of trial treatment as specified in the Trial Flow Chart.

8.1.1.10 Tumor Imaging and Assessment of Disease

Baseline and restaging radiologic imaging will be performed to encompass all sites of metastatic disease. This will generally include at least CT CAP though the specific imaging study can be changed by the treating investigator depending on patient circumstances. Radiologic imaging modality should be consistent throughout the study for response

assessment. For patients who have known bone metastases at baseline, bone scan should additionally be pursued as standard of care for disease assessment.

8.1.1.11 Tumor Tissue Collection and Correlative Studies Blood Sampling

The following tables outline the requirements for tissue and blood banking. These will be collected and stored for batched future analysis.

Biospecimen type	Collection Time Point	Number of samples per patient
Fecal sample	Pre-treatment: obtained prior treatment on protocol	2 samples
	On-treatment: obtained at dose 4 of treatment with pembrolizumab	
A paraffin-embedded tissue block of the primary tumor taken before initiation of treatment (if available).	Pre-treatment: obtained prior treatment on protocol	1 historical sample
Peripheral Blood Mononuclear Cells: ~60 ml of anti-coagulated whole blood in green top tube	Pre-treatment: 8-10 tubes taken within 21 days prior to initiation of treatment.	Up to 30 samples total over 3 time points
	Post treatment: 8-10 tubes taken day of dose 1 and dose 4 pembrolizumab and at time of progressive disease.	
Whole blood for germline DNA: 8-10 mL of whole blood in PAXgene tube	Pre-treatment: taken 21 days prior to initiation of treatment.	1 sample
Whole blood for serum analysis: 8-10 mL of whole blood in red top tube	Pre-treatment: taken within 21 days prior to initiation of treatment.	1 sample

Biospecimens will be shipped and stored in the University of Chicago Human Immune Monitoring Core Facility.

Human Immune Monitoring Core:

Product: Pembrolizumab 34

Protocol/Amendment No.:

Contact: [name]

University of Chicago - Human Immune Monitoring Core

[name]

[contact] [contact]

8.1.2 Laboratory Procedures/Assessments

Details regarding specific laboratory procedures/assessments to be performed in this trial are provided below. Laboratory Safety Evaluations (Hematology, Chemistry and Urinalysis)

Laboratory tests for hematology, chemistry, urinalysis, and others are specified in Table 5.

Table 5 Laboratory Tests

Hematology	Chemistry	Urinalysis	Other
Hematocrit	Albumin	Blood	Serum β-human chorionic gonadotropin†
Hemoglobin	Alkaline phosphatase	Glucose	(β-hCG)†
Platelet count	Alanine aminotransferase (ALT)	Protein	
WBC (total and differential)	Aspartate aminotransferase (AST)	Specific gravity	
Red Blood Cell Count	Lactate dehydrogenase (LDH)	Microscopic exam (If abnormal)	Total thriiodothyronine (T3)
Absolute Neutrophil Count	Carbon Dioxide	results are noted	Free tyroxine (T4)
Absolute Lymphocyte Count	(CO ₂ or biocarbonate)	Urine pregnancy test †	Thyroid stimulating hormone (TSH)
	Calcium		
	Chloride		Blood for correlative studies
	Creatinine		
	Glucose		
	Potassium		
	Sodium		
	Total Bilirubin		
	Direct Bilirubin (If total bilirubin is elevated above the upper limit of normal)		
	Total protein		
	Blood Urea Nitrogen		
† Perform on women of childbea	aring potential only. If urine pregnancy res	ults cannot be confirmed as negative.	a serum pregnancy test will be required.

Laboratory tests for screening or entry into the Second Course Phase should be performed within 10 days prior to the first dose of treatment. After Cycle 1, pre-dose laboratory procedures can be conducted up to 72 hours prior to dosing. Results must be reviewed by the investigator or qualified designee and found to be acceptable prior to each dose of trial treatment.

8.1.3 Other Procedures

8.1.3.1 Withdrawal/Discontinuation

When a subject discontinues/withdraws prior to trial completion, all applicable activities scheduled for the final trial visit should be performed at the time of discontinuation. Any adverse events which are present at the time of discontinuation/withdrawal should be followed in accordance with the safety requirements outlined in Section 7.2 - Assessing and Recording Adverse Events. Subjects who a) attain a CR or b) complete 24 months of treatment with pembrolizumab may discontinue treatment with the option of restarting treatment if they meet the criteria specified in Section 7.1.4.2. After discontinuing treatment following assessment of CR, these subjects should return to the site for a Safety Follow-up Visit and then proceed to the Follow-Up Period of the study.

8.1.4 Visit Requirements

Visit requirements are outlined in Section 6.0 - Trial Flow Chart. Specific procedure-related details are provided above in Section 7.1 - Trial Procedures.

The mandatory Safety Follow-Up Visit should be conducted approximately 30 days after the last dose of trial treatment or before the initiation of a new anti-cancer treatment, whichever comes first. All AEs that occur prior to the Safety Follow-Up Visit should be recorded. Subjects with an AE of Grade > 1 will be followed until the resolution of the AE to Grade 0-1 or until the beginning of a new anti-neoplastic therapy, whichever occurs first. SAEs that occur within 90 days of the end of treatment or before initiation of a new anti-cancer treatment should also be followed and recorded. Subjects who are eligible for retreatment with pembrolizumab (as described in Section 7.1.4.2) may have up to two safety follow-up visits, one after the Treatment Period and one after the Second Course Phase.

8.1.4.1 Follow-up Visits

Subjects who discontinue trial treatment for a reason other than disease progression will move into the Follow-Up Phase and should be assessed every 12 weeks (± 7 days) by radiologic imaging to monitor disease status up to 24 months after the final patients is enrolled or until receiving treatment outside of this protocol. Every effort should be made to collect information regarding disease status until the start of new anti-neoplastic therapy, disease progression, death, end of the study or if the subject begins retreatment with pembrolizumab as detailed in Section 7.1.4.2. Information regarding post-study anti-neoplastic treatment will be collected if new treatment is initiated.

Subjects who are eligible to receive retreatment with pembrolizumab according to the criteria in Section 7.1.4.2 will move from the follow-up phase to the Second Course Phase when they experience disease progression.

8.1.4.2 Second Course Phase (Retreatment Period)

Subjects who stop pembrolizumab with SD or better may be eligible for up to one year of additional pembrolizumab therapy if they progress after stopping study treatment. This retreatment is termed the Second Course Phase of this study and is only available if the study remains open and the subject meets the following conditions:

• Either

- Stopped initial treatment with pembrolizumab after attaining an investigatordetermined confirmed CR according to RECIST 1.1, and
 - Was treated for at least 24 weeks with pembrolizumab before discontinuing therapy
 - Received at least two treatments with pembrolizumab beyond the date when the initial CR was declared

OR

 Had SD, PR or CR and stopped pembrolizumab treatment after 24 months of study therapy for reasons other than disease progression or intolerability

AND

- Experienced an investigator-determined confirmed radiographic disease progression after stopping their initial treatment with pembrolizumab
- Did not receive any anti-cancer treatment since the last dose of pembrolizumab
- Has a performance status of 0 or 1 on the ECOG Performance Scale
- Demonstrates adequate organ function as detailed in Section 5.1.2
- Female subject of childbearing potential should have a negative serum or urine pregnancy test within 72 hours prior to receiving retreatment with study medication.
- Female subject of childbearing potential should be willing to use 2 methods of birth control or be surgically sterile, or abstain from heterosexual activity for the course of the study through 120 days after the last dose of study medication (Reference Section 5.7.2). Subjects of child bearing potential are those who have not been surgically sterilized or have been free from menses for > 1 year.

- Male subject should agree to use an adequate method of contraception starting with the first dose of study therapy through 120 days after the last dose of study therapy.
- Does not have a history or current evidence of any condition, therapy, or laboratory abnormality that might interfere with the subject's participation for the full duration of the trial or is not in the best interest of the subject to participate, in the opinion of the treating investigator.

Subjects who restart treatment will be retreated at the same dose and dose interval as when they last received pembrolizumab. Treatment will be administered for up to one additional year.

Visit requirements are outlined in Section 6.0 – Trial Flow Chart.

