5.1.2 Subject Inclusion Criteria

In order to be eligible for participation in this trial, the subject must:

- 1. Be willing and able to provide written informed consent for the trial.
- 2. Be \geq 18 years of age on day of signing informed consent.
- 3. Have experienced disease progression during treatment with an anti-PD1/L1 antibody as the treatment regimen immediately prior to accrual to this study or disease progression within 6 months of adjuvant anti-PD1 antibody.
- 4. Have measurable disease based on irRECIST 1.1.
- 5. Have a performance status of 0 or 1 on the ECOG Performance Scale.
- 6. Demonstrate adequate organ function as defined in Table 1.

Table 1 Adequate Organ Function Laboratory Values

System	Laboratory Value
Hematological	
Absolute neutrophil count (ANC)	≥1,500 /mcL
Platelets	≥100,000 / mcL
Hemoglobin	≥8 g/dL or ≥4.96 mmol/L
Renal	
Serum creatinine OR	≤1.5 X upper limit of normal (ULN) OR

Measured or calculated ^a creatinine clearance (GFR can also be used in place of creatinine or CrCl)	≥60 mL/min for subject with creatinine levels > 1.5 X institutional ULN
Hepatic	
Serum total bilirubin	≤ 1.5 X ULN OR
	Direct bilirubin ≤ ULN for subjects with total bilirubin levels > 1.5 ULN
AST (SGOT) and ALT (SGPT)	≤ 2.5 X ULN OR ≤ 5 X ULN for subjects with liver metastases
Albumin	≥2.5 mg/dL
^a Creatinine clearance should be calculated	per institutional standard.

- 7. Female subject of childbearing potential should have a negative urine or serum pregnancy within 72 hours prior to receiving the first dose of study medication. If the urine test is positive or cannot be confirmed as negative, a serum pregnancy test will be required.
- 8. Female subjects of childbearing potential should be willing to use 2 methods of birth control or be surgically sterile, or abstain from heterosexual activity for the course of the study through 120 days after the last dose of study medication (Reference Section 5.7.2). Subjects of childbearing potential are those who have not been surgically sterilized or have not been free from menses for > 1 year.
- 9. Male subjects should agree to use an adequate method of contraception starting with the first dose of study therapy through 120 days after the last dose of study therapy.

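### Table 1 (Section 5.1.2) gives the albumin eligibility limit in mg/dL, so the criterion as written excludes no one at initial entry or, by cross-reference, at Second Course entry

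*Combined protocol and SAP*

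**What the plan says.** Inclusion criterion 6 in Section 5.1.2 reads "Demonstrate adequate organ function as defined in Table 1". In that table the albumin row requires at least 2.5 mg/dL. The hemoglobin row of the same table is on a different scale: "≥8 g/dL or ≥4.96 mmol/L". No other section gives an albumin limit or a different unit for it.

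Section 8.1.4.2 lists the conditions for the Second Course Phase. One of them is "Demonstrates adequate organ function as detailed in Section 5.1.2", which leads back to Table 1.

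Albumin is in the chemistry column of Table 5, and the Section 6.1 flow chart schedules the chemistry panel at screening and at each treatment cycle. Section 8.1.2 sets the timing for both entry decisions: "Laboratory tests for screening or entry into the Second Course Phase should be performed within 10 days prior to the first dose of treatment".

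**The concern.** Serum albumin is a protein present in grams per decilitre, like hemoglobin, which the same table expresses in g/dL. A limit of 2.5 in mg/dL is far below any value a laboratory would report for a patient, so the criterion appears to have no effect.

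The row is operative eligibility text, not background. A site that applies the printed unit has no working albumin limit. A site that reads the row in g/dL applies a limit the protocol does not contain, and could turn away a patient who meets the written criteria. Two sites could therefore treat the same albumin value differently, and a monitor or auditor checking adherence under Sections 12.4 and 12.5 has no usable figure to check against.

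At initial entry there is also a link to the analysis, because Section 10.1 limits evaluable patients to eligible ones who receive a dose of the combination. The written definition of eligible should therefore be usable.

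**Working it through.** **Inputs**

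- Albumin limit: 2.5 mg/dL (Section 5.1.2, Table 1).
- Hemoglobin limit: 8 g/dL or 4.96 mmol/L (same table).
- Range of measurable serum albumin: not in the documents; assumed to be 0.5 to 5.5 g/dL.
- Unit conversion: 1 g/dL = 1,000 mg/dL.

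The albumin limit is stated without a derivation, so there is no calculation in the plan to reproduce.

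**Step 1. Convert the printed limit.** 2.5 mg/dL ÷ 1,000 = 0.0025 g/dL.

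**Step 2. Compare it with albumin values across the assumed range.**

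| Albumin (g/dL) | In mg/dL | Ratio to printed limit | Meets the row? |
|---|---|---|---|
| 0.5 | 500 | 500 ÷ 2.5 = 200 | yes |
| 1.5 | 1,500 | 1,500 ÷ 2.5 = 600 | yes |
| 2.5 | 2,500 | 2,500 ÷ 2.5 = 1,000 | yes |
| 3.5 | 3,500 | 3,500 ÷ 2.5 = 1,400 | yes |
| 5.5 | 5,500 | 5,500 ÷ 2.5 = 2,200 | yes |

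Every value passes, including the lowest. The conclusion is not sensitive to the assumed range: its lower end would have to fall 200-fold before any patient failed.

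**Step 3. Check whether the whole table is affected.** With an assumed conversion factor of 0.6206 mmol/L per g/dL, hemoglobin gives 8 × 0.6206 = 4.9648, which rounds to the printed 4.96 mmol/L. The hemoglobin row is internally consistent, so this check gives no sign of a table-wide unit problem.

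**Step 4. Size of the discrepancy under one reading.** If the same number in g/dL was intended, that limit is 2,500 mg/dL and the printed one is 2,500 ÷ 2.5 = 1,000 times too low. The documents do not confirm that reading. Purely to show the range, limits of 2.0 to 3.5 g/dL would be 800 to 1,400 times the printed one.

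**Step 5. Where the row takes effect.** It applies directly through inclusion criterion 6. It applies a second time through Section 8.1.4.2, whose reference to Section 5.1.2 points to the right place.

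**Step 6. Effect on the design.** The two-stage design in Section 10.1 rests on response rates of 10% and 30%, stages of 12 and 23 patients, and its response boundaries. Albumin enters none of these.

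**The case against.** The best defence is that the slip is obvious and the protocol has other safeguards. Under Section 7.2 the coordinating CRA receives source documents before treatment starts and takes eligibility questions to the PI, who may clarify criteria but not overturn them. Exclusion criterion 13 lets the investigator keep out a patient for a laboratory abnormality. The last Second Course condition does the same at retreatment: "Does not have a history or current evidence of any condition, therapy, or laboratory abnormality that might interfere with the subject's participation". Section 8.1.2 also requires laboratory results to be reviewed and found acceptable before each dose.

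Much of this stands, and it limits the practical effect. A patient with an albumin of 1.5 g/dL meets the albumin row but is not thereby cleared for treatment. What the safeguards do not do is supply a number. They are discretionary and can differ between sites, and the clarification route works only if someone raises the question. They leave the row itself without effect.

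Several stronger readings are tempting, and the documents do not support them:

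- A reader might infer that the retreatment section is at fault. It is not; its cross-reference is correct and it only inherits the Table 1 unit.
- A reader might infer that the retreatment check alters the evaluable set in Section 10.1. Second Course subjects have already entered the trial and been dosed, so that link concerns initial entry alone.
- A reader might infer from Section 7.2 that sites must document albumin against the printed figure. The section asks for source documents that support each criterion, which is less than that.
- A reader might infer a biased response rate or a known number of wrongly admitted patients. The documents give no albumin distribution and no evidence of how sites read the row, so neither can be shown.

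**Conclusion.** The point holds as a unit error in one row of Table 1. Followed exactly as written, the albumin criterion excludes no one, both at initial entry and, by inheritance, at Second Course entry. This rests on taking the printed unit at face value and on the assumed range of 0.5 to 5.5 g/dL for measurable albumin.

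The factor of 1,000 is conditional on the same number in g/dL having been intended, which only the sponsor can confirm. How many patients would fail a corrected limit is unknown.

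The importance is minor. The sample size, stopping boundaries, error rates and power are untouched, and discretionary checks may still stop a patient with low albumin. It is nevertheless worth correcting, because an eligibility threshold that cannot be applied or audited should not remain in the protocol.

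**What to change.** The sponsor should check the albumin row of Table 1 against its source, confirm the intended limit and unit, and correct the unit. The eligibility checklist is not among the documents; if it repeats the figure, it should be corrected at the same time. Section 8.1.4.2 needs no change, since its reference to Section 5.1.2 will then carry the corrected limit into the Second Course Phase and both entry decisions will use one valid figure.

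The cost is one unit in a table, handled through the amendment procedure in Section 12.6. The downside is that any patient below the corrected limit, who is admissible as the table now stands, would no longer qualify.
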